# 10.1.4 Supportive analyses

For each primary endpoint, the regression models detailed in section 10.1.2 will be performed for supportive purposes:

- by considering complete cases only (i.e. without considering patients with missing primary endpoint).
- on the PP set instead of FAS.

# **10.2** Analysis of secondary efficacy endpoints

10.2.1 Testing strategy and multiplicity adjustment

In case the analysis of the primary endpoints leads to rejection of null hypothesis, some secondary endpoints (defined as key secondary endpoints) will be tested in a conditional sequential manner to show superiority of cenegermin versus control (at alpha one-sided 0.025) according to the following ranking:

- 1. Proportion of patients reaching a value of Schirmer I test (without anesthesia) >10mm/5min at week 8.
- 2. Change from baseline in SANDE scores for severity at week 12.
- 3. Change from baseline in SANDE scores for frequency at week 12.
- 4. Change from baseline in IDEEL modules (Quality of Life [27 questions], Dry eye Treatment satisfaction & Bother [10 questions], and Dry eye Symptom bother [20 questions]) at week 12 and at week 4 (in this order).
- 5. Change from baseline in Cornea and conjunctiva vital staining with fluorescein NEI scale at week 4, week 8 and at week 12 (in this order).
- 6. Change from baseline in TFBUT at week 4, week 8 and at week 12 (in this order).

This hierarchical test strategy protects the family-wise false positive error rate at the overall onesided 0.025 level.

# 10.2.2 Analysis details

Analysis of key secondary endpoints are detailed below in sections 10.2.2.1 - 10.2.2.6 and p-values to be evaluated for comparison between treatments in a sequential order are the following:

- 1. P-value of treatment variable from logistic regression model on proportion of patients reaching a value of Schirmer I test (without anesthesia) >10mm/5min at week 8 (section 10.2.2.1),
- 2. P-value of treatment variable from ANCOVA regression model on change from baseline in SANDE score for severity at week 12 (section 10.2.2.2),
- 3. P-value of treatment variable from ANCOVA regression model on change from baseline in SANDE score for frequency at week 12 (section 10.2.2.3),
- 4.1 P-value of treatment variable from MMRM regression model on IDEEL Quality of Life module at week 12 (section 10.2.2.4),
- 4.2 P-value of treatment variable from MMRM regression model on IDEEL Dry eye Treatment satisfaction & Bother module at week 12 (section 10.2.2.4),

- 4.3 P-value of treatment variable from MMRM regression model on IDEEL Dry eye Symptom bother module at week 12 (section 10.2.2.4),
- 4.4 P-value of treatment variable from MMRM regression model on IDEEL Quality of Life module at week 4 (section 10.2.2.4),
- 4.5 P-value of treatment variable from MMRM regression model on IDEEL Dry eye Treatment satisfaction & Bother module at week 4 (section 10.2.2.4),
- 4.6 P-value of treatment variable from MMRM regression model on IDEEL Dry eye Symptom bother module at week 4 (section 10.2.2.4),
- 5.1 P-value of treatment variable from MMRM regression model on Change from baseline in Cornea and conjunctiva vital staining with fluorescein NEI scale at week 4 (section 10.2.2.5),
- 5.2 P-value of treatment variable from MMRM regression model on Change from baseline in Cornea and conjunctiva vital staining with fluorescein NEI scale at week 8 (section 10.2.2.5),
- 5.3 P-value of treatment variable from MMRM regression model on Change from baseline in Cornea and conjunctiva vital staining with fluorescein NEI scale at week 12 (section 10.2.2.5),
- 6.1 P-value of treatment variable from MMRM regression model on Change from baseline in TFBUT values at week 4 (section 10.2.2.6),
- 6.2 P-value of treatment variable from MMRM regression model on Change from baseline in TFBUT values at week 8 (section 10.2.2.6),
- 6.3 P-value of treatment variable from MMRM regression model on Change from baseline in TFBUT values at week 12 (section 10.2.2.6).

# 10.2.2.1 Schirmer I test >10mm/5min at week 8

The proportion of patients reaching a value of Schirmer I test (without anesthesia) >10mm/5min at week 8 will be analyzed as described in section 10.1.2.1 for the primary efficacy endpoints.

# 10.2.2.2 Change from baseline in SANDE score for severity at week 12

The change from baseline in SANDE score for severity at week 12 will be analyzed as described in section 10.1.2.2 for the primary efficacy endpoints.

# 10.2.2.3 Change from baseline in SANDE scores for frequency at week 12

The change from baseline in SANDE score for frequency at week 12 will be analyzed as described in section 10.1.2.2 for the primary efficacy endpoints.

# 10.2.2.4 Change from baseline in IDEEL modules (Quality of Life, Dry eye Treatment satisfaction & Bother, and Dry eye Symptom bother) at week 12 and at week 4

Rules for derivation of IDEEL scores are reported in section 12.3. The change from baseline of each IDEEL module will be analyzed by means of an MMRM adjusting by pre-defined factors (gender, age class, IDEEL module baseline value, treatment, visit, and treatment by visit interaction; subject will be considered as a random effect). The covariance matrix used will be "unstructured". Comparisons versus vehicle TID will be provided using least square means at each visit and overall and a one-sided test will be used to test for differences between treatment groups.

For the imputation of missing data, a regression model will be created by including the baseline value, gender, age class, and intermediate scores up to week 12. Two hundred data sets will be generated, and the random seed number will be 225670. MI will be implemented in the following steps:

- 1. Partial imputation assuming MAR will be carried out to impute intermittent (non-monotone) missing data of IDEEL module score based on a multivariate joint Gaussian imputation model using the MCMC method. A separate imputation model will be used for each treatment arm. In case of non-convergence or non-estimability issues, a single imputation model will be considered (with treatment arm added as explanatory variable to the model). A total of 200 datasets will be created. These datasets will be utilized in Step #2.
- 2. The remaining monotone missing data will be imputed using a MI regression including the same explanatory variables of the previous step. According to MI-RD approach, only non-missing values from retrieve dropouts will be used to inform the regression model.
- 3. Each of the 200 imputed datasets will be analyzed using observed and imputed data. Rubin's rule will be used for combining results to draw inference.

If there are not enough retrieved dropouts for convergence of MI-RD regression model, a Copy Reference approach will be adopted to consider a MNAR mechanism for missing data. The final decision on the use of the MI-RD vs Copy-Reference for this endpoint will be done at the time of the analysis and reported in the CSR.

Whether for MI-RD or Copy-Reference approach, the adjusted estimated treatment differences in means for IDEEL module scores between cenegermin and vehicle at each available timepoint will be displayed together with the corresponding two-side 95% confidence intervals and p-value.

# 10.2.2.5 Change from baseline in Cornea and conjunctiva vital staining with fluorescein NEI scale at week 4, week 8 and at week 12

Rules for derivation of NEI scores are reported in section 12.4. The change from baseline in Cornea and conjunctiva vital staining with fluorescein NEI scale will be analyzed by means of an MMRM adjusting by pre-defined factors (gender, age class, NEI scale baseline value, treatment, visit, and treatment by visit interaction; subject will be considered as a random effect). The covariance matrix used will be "unstructured". Comparisons versus vehicle TID will be provided using least square means at each visit and overall and a one-sided test will be used to test for differences between treatment groups.

For the imputation of missing data, a regression model will be created by including the baseline value, gender, age class, and intermediate scores up to week 12. Two hundred data sets will be generated, and the random seed number will be 569888. MI will be implemented in the following steps:

- 1. Partial imputation assuming MAR will be carried out to impute intermittent (non-monotone) missing data of NEI scale score based on a multivariate joint Gaussian imputation model using the MCMC method. A separate imputation model will be used for each treatment arm. In case of non-convergence or non-estimability issues, a single imputation model will be considered (with treatment arm added as explanatory variable to the model). A total of 200 datasets will be created. These datasets will be utilized in Step #2.
- 2. The remaining monotone missing data will be imputed using a MI regression including the same explanatory variables of the previous step. According to MI-RD approach, only non-missing values from retrieve dropouts will be used to inform the regression model.
- 3. Each of the 200 imputed datasets will be analyzed using observed and imputed data. Rubin's rule will be used for combining results to draw inference.

If there are not enough retrieved dropouts for convergence of MI-RD regression model, a Copy Reference approach will be adopted to consider a MNAR mechanism for missing data. The final decision on the use of the MI-RD vs Copy-Reference for this endpoint will be done at the time of the analysis and reported in the CSR.

Whether for MI-RD or Copy-Reference approach, the adjusted estimated treatment differences in means for NEI scale scores between cenegermin and vehicle at each available timepoint will be displayed together with the corresponding two-side 95% confidence intervals and p-value.

## 10.2.2.6 Change from baseline in TFBUT at week 4, week 8 and at week 12

The change from baseline in TFBUT values will be analyzed by means of a MMRM adjusting by pre-defined factors (gender, age class, TFBUT baseline value, treatment, visit, and treatment by visit interaction; subject will be considered as a random effect). The covariance matrix used will be "unstructured". Comparisons versus vehicle TID will be provided using least square means at each visit and overall and a one-sided test will be used to test for differences between treatment groups.

For the imputation of missing data, a regression model will be created by including the baseline value, gender, age class, and intermediate scores up to week 12. Two hundred data sets will be generated, and the random seed number will be 101149. MI will be implemented in the following steps:

- 1. Partial imputation assuming MAR will be carried out to impute intermittent (non-monotone) missing data of TFBUT values based on a multivariate joint Gaussian imputation model using the MCMC method. A separate imputation model will be used for each treatment arm. In case of non-convergence or non-estimability issues, a single imputation model will be considered (with treatment arm added as explanatory variable to the model). A total of 200 datasets will be created. These datasets will be utilized in Step #2.
- 2. The remaining monotone missing data will be imputed using a MI regression including the same explanatory variables of the previous step. According to MI-RD approach, only non-missing values from retrieve dropouts will be used to inform the regression model.
- 3. Each of the 200 imputed datasets will be analyzed using observed and imputed data. Rubin's rule will be used for combining results to draw inference.

If there are not enough retrieved dropouts for convergence of MI-RD regression model, a Copy Reference approach will be adopted to consider a MNAR mechanism for missing data. The final decision on the use of the MI-RD vs Copy-Reference for this endpoint will be done at the time of the analysis and reported in the CSR.

Whether for MI-RD or Copy-Reference approach, the adjusted estimated treatment differences in means for NEI scale scores between cenegermin and vehicle at each available timepoint will be displayed together with the corresponding two-side 95% confidence intervals and p-value.

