#### 9.4.3.3. Secondary analyses

In case analysis of the co-primary endpoints leads to rejection of null hypothesis, the following key secondary endpoints will be tested in a conditional sequential manner to show superiority of cenegermin versus control (at alpha one-sided 0.025) according to the following ranking:

 Proportion of patients reaching a value of Schirmer I test (without anesthesia) >10mm/5min at week 8;

- 2. Change from baseline in SANDE scores for severity at week 12;
- 3. Change from baseline in SANDE scores for frequency at week 12;
- 4. IDEEL modules (Quality of Life [27 questions], Dry eye Treatment satisfaction & Bother [10 questions], and Dry eye Symptom bother [20 questions]) at week 12 and at week 4 (in this order);
- 5. Change from baseline in Cornea and conjunctiva vital staining with fluorescein NEI scales at week 4, week 8 and at week 12 (in this order);
- 6. Change from baseline in TFBUT at week 4, week 8 and at week 12 (in this order).

This hierarchical test strategy protects the family-wise false positive error rate at the overall one-sided 0.025 level.

Key secondary endpoint #1, will be analyzed as detailed in section 9.4.3.1.

Key secondary endpoints #2 - #6 will be analyzed by means of an ANCOVA model adjusting by pre-defined baseline factors (site, gender, age class, corresponding baseline value). Missing data will be imputed according to MI-RD (or wash-out approach, see section 9.4.3.1).

In case of not rejection of null hypothesis, the above test strategy will not be performed. Instead, independently of results on primary endpoint, descriptive in nature analyses will be performed on all secondary endpoints at each available timepoints by means of descriptive statistics and by appropriate parametric tests depending on the nature of the variable and its distribution.

Data transformation might be used in order to satisfy the assumption of normality requested by parametric statistical tests. In case such assumptions are not met, non-parametric counterpart tests will be used. Change from baseline value (for continuous variables) and shift tables versus baseline (for categorical variables) will also be summarized for all post-baseline visits.

Further details will be provided in the SAP.

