# 6. Randomization and blinding

#### 6.1.1 Randomization

Eligible patients will be randomized in a 1:1 ratio to either cenegermin ophthalmic solution 20 mcg/mL TID or vehicle ophthalmic solution TID.

Randomization will be stratified by site to ensure balanced assignment across treatment groups. The stratified permuted block randomization list will be generated with a computer procedure by an independent statistician not involved in the conduct of the study.

Randomization will be performed through IRS. Each Patient Kit number will be randomly associated with a treatment group. The randomization list will be provided to the facility responsible for IMP packaging/labelling for the purpose of IMP preparation. Each randomized patient will be allocated with randomization number according to the stratified randomization list. Dropouts after randomization will not be replaced.

The enrollment of patients will be scheduled in order to assure an inclusion of approximately 80 patients to ensure at least 72 patients assuming up to 10% of patients not evaluable after enrollment.

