#### 7.8 Handling of missing and incomplete data

All reasonable efforts will be made to reduce the rate of missing data. Investigators will be trained about the importance of patient retention and full data capture. Also, any reasonable attempts should be made by the investigators to emphasize continued subject's participation for the full duration of the trial.

Patients who discontinue the treatment will not be withdrawn from the study by default but will be asked to complete safety and efficacy observations as per the protocol, unless otherwise they withdraw their consent. Patients who discontinue study treatment and decide to remain in the study

by following the schedule of assessments and continuing to adhere to protocol requirements are defined as "retrieved drop-out" patients.

For the primary and key secondary analyses, missing data will be handled by means of Multiple Imputation using retrieve dropouts (MI-RD), as detailed in sections 10.1.2 and 10.2.2.

In addition, to further minimize missing data, if a patient cannot refer to the site for a planned followup visit, the investigator will try to obtain any relevant information from the patients, including documents/laboratory results available from local medical care.

The number of subjects with missing data will be presented under the "Missing" category. Missing values will not be included in the denominator count when computing percentages. When continuous data will be summarized, only the non-missing values will be evaluated for computing summary statistics.

For the analyses of parameters for which an independent blinded reading center may be involved per protocol, the following rules will be used:

- 1. If assessment from blinded reading center is available, such value will be used for the analysis.
- 2. If assessment form blinded reading center is not available, the corresponding evaluation (if any) from the site investigator will be used.
- 3. If both assessments (blinded reading center and site investigator) are not available, a statistical imputation method will be applied as described in this SAP.

Rules for handling missing data of IDEEL questionnaire are reported in section 12.3, according to the dedicated manual.

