# 7.9 Changes in the planned analysis

The following changes have been included, compared to the protocol [1]:

- In the secondary endpoint on SANDE, the global score has been included (section 3.2.2) in addition to severity and frequency scores.
- A clarification on the use of data from blinded reading center and site investigator has been added in section 7.8.
- The first key secondary endpoint in section 10.2.1 has been reworded in alignment with the definition of the Schirmer I test primary endpoint.
- A clarification on the use of a Mixed Model for Repeated Measurements (MMRM), extension of ANCOVA for repeated measurements, after imputation through MI-RD for IDEEL, NEI scale and TFBUT endpoints has been added in section 10.2.2, in alignment with treatment policy estimand used for primary endpoints.
- Considering the progress of data collection, the overview of planned statistical analyses (section 6.2) has been updated compared to protocol. A single database lock will be performed at the end of the study (instead of two locks), followed by the release of the KFR and by the final analyses. This decision represents a conservative choice in favor of the integrity of the study.

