If there are not enough retrieved dropouts for convergence of MI-RD regression model, a referencebased Multiple Imputation (MI) approach will be adopted to consider a missing not at random (MNAR) mechanism for missing data: imputation of values in the rhNGF arm (above step #2) will be done using the non-missing values from the control group (this approach will be referred as "Copy Reference"). This approach does not assume benefits for rhNGF in case of discontinuation and limits a post-discontinuation clinical effect to that of vehicle. The final decision on the use of the MI-RD vs Copy-Reference for this endpoint will be done at the time of the analysis and reported in the CSR.

Whether for MI-RD or Copy-Reference approach, the adjusted estimated treatment differences in proportions between cenegermin and vehicle at week 4 will be displayed together with the corresponding two-side 95% confidence intervals and p-value.

### 10.1.2.2 Change from baseline in the global SANDE score at week 12

This co-primary endpoint will be analyzed by means of an Analysis of Covariance (ANCOVA) adjusting by pre-defined baseline factors (gender, age class, baseline global SANDE score as fixed effects and site as random effect) and a one-sided test will be used to test for differences between treatment groups. Rules for derivation of SANDE scores are reported in section 12.2.

For the imputation of missing data, a regression model will be created by including the baseline global SANDE score, gender, age class, and intermediate global SANDE scores up to week 12. Two hundred data sets will be generated, and the random seed number will be 252404. MI will be implemented in the following steps:

- 1. Partial imputation assuming MAR will be carried out to impute intermittent (non-monotone) missing data of global SANDE score based on a multivariate joint Gaussian imputation model using the MCMC method. A separate imputation model will be used for each treatment arm. In case of non-convergence or non-estimability issues, a single imputation model will be considered (with treatment arm added as explanatory variable to the model). A total of 200 datasets will be created. These datasets will be utilized in Step #2.
- 2. The remaining monotone missing data will be imputed using a MI regression including the same explanatory variables of the previous step. According to MI-RD approach, only non-missing values from retrieve dropouts will be used to inform the regression model.

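### The repeated-measures models for IDEEL, NEI staining and TFBUT (12 of the 15 ordered key secondary tests) leave out site, the stratification factor, and SAP 7.9 does not record the omission

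*SAP*

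**What the plan says.** Both documents make site the only stratification factor; SAP 6.1.1 states "Randomization will be stratified by site to ensure balanced assignment across treatment groups". Protocol 9.4.3.3 specifies ANCOVA for key secondary endpoints 2 to 6, "adjusting by pre-defined baseline factors (site, gender, age class, corresponding baseline value". IDEEL, NEI staining and TFBUT are endpoints 4, 5 and 6 in that ranking.

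The SAP's own models differ in how they treat site:

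- **Schirmer and SANDE (co-primaries, SAP 10.1.2).** Site is a random effect in both. For SANDE the adjustment is "gender, age class, baseline global SANDE score as fixed effects and site as random effect". Key secondaries 1 to 3 refer back to these models, so they keep site.
- **IDEEL (10.2.2.4).** An MMRM "adjusting by pre-defined factors (gender, age class, IDEEL module baseline value, treatment, visit, and treatment by visit interaction".
- **NEI staining (10.2.2.5).** An MMRM with "gender, age class, NEI scale baseline value, treatment, visit, and treatment by visit interaction".
- **TFBUT (10.2.2.6).** An MMRM with "gender, age class, TFBUT baseline value, treatment, visit, and treatment by visit interaction".

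In the last three, subject is the only random effect named. SAP 7.9 does list the change of model for these endpoints, as "A clarification on the use of a Mixed Model for Repeated Measurements (MMRM), extension of ANCOVA for repeated measurements", but it does not mention site. The SAS code in SAP 15.4 covers only the co-primaries, so it does not put site back.

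**The concern.** When allocation is balanced within site, the treatment difference is estimated largely within sites, and differences between sites mostly cancel out of it. A model without site does not use this. It counts between-site variance as noise and reports a standard error that is too large. The test becomes conservative and loses power.

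The key secondary tests form a fixed sequence at one-sided 0.025. From test 4.1 onwards, an avoidable miss ends confirmatory testing of everything after it.

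There is also a matter of record. Someone reading SAP 7.9 would take the MMRM to be the protocol's ANCOVA carried over to repeated measurements with its covariates intact. If the gap is noticed only after unblinding, both adding site and defending its absence could look driven by the results.

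**Working it through.** **1. Number of tests affected.** SAP 10.2.2 lists tests 1, 2 and 3 (3 tests), 4.1–4.6 (6), 5.1–5.3 (3) and 6.1–6.3 (3): 3 + 6 + 3 + 3 = 15. The MMRM tests number 6 + 3 + 3 = 12.

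**2. The plan's own power figures.** SAP 5 states power for the co-primaries only, with 36 evaluable patients per arm and one-sided alpha 0.025.

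- Schirmer, 75% against 33%: pooled proportion 0.54, standard error 0.1175 under the null and 0.1065 under the alternative. Φ[(0.42 − 1.96 × 0.1175)/0.1065] = 96.3%; stated 96.3%.
- SANDE, 10 points with SD 12: Φ[10/(12√(2/36)) − 1.96] = Φ(3.536 − 1.96) = 94.2%; stated 94.1%.

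Both reproduce. Neither depends on the MMRMs, and no power is stated for IDEEL, NEI or TFBUT.

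**3. Effect of omitting site, closed form.** Let r be the site share of residual variance. The documents give no value, so a range is assumed. The premise is that the true sampling variance of the treatment difference is the within-site variance and only the reported standard error is inflated.

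- Standard error inflation = 1/√(1 − r)
- True one-sided alpha = P(Z > 1.96/√(1 − r))
- Power of a test that would have 80% = Φ(1.96 + 0.8416 − 1.96/√(1 − r))

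| Assumed r | SE too large by | True alpha | Power |
|---|---|---|---|
| 0.02 | 1.0% | 0.024 | 79.4% |
| 0.05 | 2.6% | 0.022 | 78.5% |
| 0.10 | 5.4% | 0.019 | 76.9% |
| 0.20 | 11.8% | 0.014 | 72.9% |

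Example at r = 0.10: 1.96/√0.90 = 2.066; P(Z > 2.066) = 0.019; Φ(2.8016 − 2.066) = Φ(0.736) = 76.9%.

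**4. Simulation check.** The 80 patients and 10 sites follow the protocol's approximate figures. Equal sites of 8, permuted blocks of 4, a single time point and fixed site effects standing in for random ones are assumptions. There were 20,000 runs per scenario.

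| Assumed r | Null rejection, without site | Null rejection, with site | Power, without site | Power, with site |
|---|---|---|---|---|
| 0.05 | 0.023 | 0.026 | 77.9% | 79.1% |
| 0.10 | 0.018 | 0.023 | 76.2% | 79.1% |
| 0.20 | 0.016 | 0.025 | 72.5% | 78.9% |

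The simulation agrees with the closed form: conservative without site, close to nominal with it.

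**5. Sensitivity to the set-up.** With a larger assumed effect (0.8 SD, 4:4 within each site, 40,000 runs), power without and with site is 95.2% and 96.1% at r = 0.10, and 96.1% and 97.6% at r = 0.20. With unequal sites (assumed 20 patients down to 2, 5,000 runs), it is 77.3% and 77.4% at r = 0.05, 76.0% and 77.9% at 0.10, and 71.4% and 76.7% at 0.20.

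**The case against.** The strongest reply is that this cannot harm validity. Type I error is not inflated, the co-primaries and tests 1 to 3 are untouched, and the affected tests carry confirmatory weight only if all of those succeed. That is correct and limits how serious the point can be.

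The size also rests on an assumed variance. For NEI, SAP 7.8 says "If assessment from blinded reading center is available, such value will be used for the analysis", and IDEEL is reported by the patient, so site variance is probably small for 9 of the 12 tests (6 + 3). Baseline adjustment removes part of any stable site difference as well. At r of 0.02 to 0.05 the loss from 80% is 0.6 to 1.5 percentage points, and the loss is smaller where starting power is higher. This stands, and the power figures should be read as illustrations.

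On disclosure, the SAP prints the full covariate lists and names the change of model, and the protocol leaves further detail to the SAP. The models are therefore visible and pre-specified. But 7.9 is where departures from the protocol are listed, and the loss of a covariate the protocol names is not there.

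Finally, a random site intercept with about 10 sites will sometimes be estimated at zero. In a single-time-point check this happened in about 44% of datasets at r = 0.02 and 30% at r = 0.05, with power gains of about 1 to 1.5 points at those values and about 3 points at r = 0.10. This does not count against the term: with a zero estimate the model reduces to the one the SAP already specifies. A sentence on degrees of freedom and on non-convergence would be useful detail.

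**Conclusion.** The concern holds. Twelve of the 15 ordered key secondary tests use models that omit the stratification factor. This departs from Protocol 9.4.3.3, is inconsistent with the SAP's own Schirmer and SANDE models, and is not recorded in SAP 7.9. No reason for the difference is given.

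The consequence is lost efficiency and an incomplete record of changes. Family-wise error control is not threatened. The loss per test is probably small for IDEEL and NEI and could be larger for TFBUT if site variance is substantial there. The estimates assume r between 0.02 and 0.20 and a starting power of 80%, neither of which the documents supply. The simulations are single-time-point approximations to the planned repeated-measures analysis. The point should be corrected because the correction costs almost nothing and the trial would then be analysed by the factor it randomises on.

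**What to change.** Before unblinding, add site as a random intercept to the three MMRMs in SAP 10.2.2.4 to 10.2.2.6, using the RANDOM INTERCEPT statement with SITEID as subject that the SAP already uses for SANDE (15.4.2). If site is left out on purpose, list that and the reason in SAP 7.9.

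As a wording clarification only, state that within-subject correlation is modelled through the unstructured repeated covariance by subject, without a separate random subject effect.

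The cost is one model term in three models and one clarifying sentence. No new data are needed, and no stated sample size or power figure changes.

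### The MMRMs for IDEEL, NEI and TFBUT impose one baseline slope on all visits; a baseline-by-visit term would protect week-12 precision at almost no cost

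*SAP*

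**What the plan says.** Protocol 9.4.3.3 sets the model for the lower key secondary endpoints: "Key secondary endpoints #2 - #6 will be analyzed by means of an ANCOVA model adjusting by pre-defined baseline factors", the factors being site, gender, age class and the baseline value of the same measure. The endpoints are listed by week, so each comparison is an ANCOVA at one week with its own baseline coefficient.

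The SAP replaces this with an MMRM for three endpoints. Besides gender and age class the terms are:

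- IDEEL (10.2.2.4): "IDEEL module baseline value, treatment, visit, and treatment by visit interaction; subject will be considered as a random effect"
- NEI (10.2.2.5): "NEI scale baseline value, treatment, visit, and treatment by visit interaction; subject will be considered as a random effect"
- TFBUT (10.2.2.6): "TFBUT baseline value, treatment, visit, and treatment by visit interaction; subject will be considered as a random effect"

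In all three, "The covariance matrix used will be" unstructured. The only interaction with visit is that of treatment. Site is not listed. SAP 7.9 discloses the MMRM and presents it as a clarification and an extension of ANCOVA. It mentions neither the common slope nor the loss of site. The SAS code in SAP 15.4 covers only the co-primaries, so it does not supply the missing term.

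In the testing order of SAP 10.2.2, the MMRM block opens with three IDEEL tests at week 12 (4.1-4.3), then three at week 4 (4.4-4.6), then NEI (5.1-5.3) and TFBUT (6.1-6.3) at weeks 4, 8 and 12.

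**The concern.** An MMRM with baseline as a main effect only is more restrictive than the ANCOVA it replaces. It is fitted to completed, multiply imputed data sets, so it has no missing-data advantage to set against the restriction. Study treatment ends at week 4 and the artificial-tear regimen changes after that, so a weaker link between baseline and outcome by week 12 is plausible. A slope pooled over visits would then adjust the week-12 comparison imperfectly.

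The position of these tests adds some weight. The hierarchy is strictly sequential, so failure at any of 4.1-4.3 ends formal testing of everything below, including all NEI and TFBUT tests.

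There is also a smaller specification problem. A random subject effect beside an unstructured within-patient covariance is redundant: its variance cannot be separated from the unstructured matrix. Each model is fitted to 200 imputed data sets, and the SAP gives non-convergence fallbacks for the imputation steps only.

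**Working it through.** **Figures in the plan.** SAP section 5 states power for the co-primaries only, with 36 evaluable patients per arm and one-sided alpha 0.025.

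- Schirmer, 33% v 75%: (0.42 - 1.96 x sqrt(2 x 0.54 x 0.46/36)) / sqrt((0.33 x 0.67 + 0.75 x 0.25)/36) = 1.78, power 96.3% (stated 96.3%).
- SANDE, difference 10, SD 12: 10/(12 x sqrt(2/36)) - 1.96 = 1.58, power 94.2% (stated 94.1%).
- Joint, if independent: 90.7% (stated 90%).

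These reproduce and do not depend on the point made here. The documents give no SD, slope or between-visit correlation for IDEEL, NEI or TFBUT, so the correlations below are assumptions.

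**Formula.** On complete data, the estimate at visit t is the difference in mean change minus b times the baseline difference. Let beta_t be the true slope at visit t and S the residual covariance given baseline. With an unstructured covariance the common slope converges to

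b = (1'S^-1 beta) / (1'S^-1 1).

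The variance relative to an ANCOVA with its own slope is then

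1 + (beta_t - b)^2 x var(baseline) / S_tt.

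This is never below 1, and equals 1 when the slope is the same at every visit.

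**Worked case.** Take unit SDs and correlation 0.90 per week. At week 12 the correlation with baseline is 0.90^12 = 0.282. The slope for change is 0.282 - 1 = -0.718, and S_tt = 1 - 0.282^2 = 0.920.

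- Weeks 2, 4, 8, 12: b = -0.313, ratio 1 + 0.405^2/0.920 = 1.178.
- Weeks 4, 8, 12: b = -0.469, ratio 1 + 0.249^2/0.920 = 1.067.

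**Range.** Increase in week-12 variance, with d the distance in weeks. The last column gives the power, with all four visits in the model, of a test that has 80% under visit-specific ANCOVA.

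| Assumed correlation | Weeks 2, 4, 8, 12 | Weeks 4, 8, 12 | Power |
|---|---|---|---|
| Constant, 0.3 to 0.7 | 0% | 0% | 80% |
| 0.3 + 0.4exp(-d/6) | 1.9% | 0.7% | 79% |
| 0.2 + 0.6exp(-d/6) | 4.4% | 1.6% | 78% |
| Linear, 0.75 at 2 weeks to 0.40 at 12 | 8.0% | 4.3% | 77% |
| AR(1), 0.7 per visit | 10.3% | 2.3% | 76% |
| AR(1), 0.95 per week | 14.6% | 6.9% | 75% |
| Linear, 0.80 at 2 weeks to 0.30 at 12 | 17.6% | 9.6% | 73% |
| AR(1), 0.90 per week | 17.8% | 6.7% | 73% |

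At week 4 the same formula gives at most about 1% with week 2 in the model and about 3% without it.

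**Simulation** (36 per arm, weeks 2, 4, 8 and 12, 4,000 trials per scenario):

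| Scenario | Week-12 variance ratio | Power, ANCOVA / MMRM |
|---|---|---|
| Constant 0.5 | 0.995 | 78.0% / 78.6% |
| 0.3 + 0.4exp(-d/6) | 1.007 | 77.4% / 78.0% |
| 0.2 + 0.6exp(-d/6) | 1.042 | 78.2% / 77.0% |
| AR(1), 0.7 per visit | 1.085 | 79.8% / 76.3% |
| AR(1), 0.8 per visit | 1.131 | 78.8% / 74.2% |

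One-sided type I error was 2.5-2.8% for the common-slope MMRM and 2.4-2.8% for ANCOVA in the same runs.

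**The case against.** The strongest reply is that a baseline main effect is a defensible, pre-specified choice, that SAP 7.9 discloses the MMRM, and that nothing in the documents shows the slope to vary. That stands, and it limits the point in several ways.

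- A reader might infer that precision is certainly lost at week 12. The documents do not support this. The end of treatment at week 4 does not by itself change the baseline slope, and with constant slopes there is no loss. In the two mildest simulated scenarios the MMRM did marginally better, within simulation noise, so one cannot say that the restriction always costs something.
- A reader might infer that the first six MMRM tests are all exposed. Only 4.1-4.3 are at week 12; 4.4-4.6 are at week 4, where little is lost. NEI and TFBUT also open at week 4.
- The larger figures need week 2 in the model. IDEEL is collected at week 2, but its endpoint time frame starts at week 4; for NEI and TFBUT, week 2 is exploratory. The SAP table titles say only that the models run up to week 12. Leaving week 2 out cuts the loss by roughly half or more in most scenarios.
- A reader might put the whole difference from the protocol's model down to the slope. The protocol specified an "ANCOVA model adjusting by pre-defined baseline factors (site, gender, age class, corresponding baseline value"), whereas the MMRM also drops site and holds gender and age effects common over visits. The calculation isolates the slope only.

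None of this supplies the missing term or gives a reason to leave it out.

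**Conclusion.** The point holds as a cheap improvement in efficiency. As written, the three MMRMs share one baseline slope over visits, and the protocol's ANCOVA at a named week does not. The possible cost falls on the week-12 comparisons: tests 4.1-4.3, and later 5.3 and 6.3. It ranges from nothing to about 18% of variance with weeks 2, 4, 8 and 12 in the model. Without week 2 it is about 0-7%, or up to about 10% under a steep linear decline. A week-12 test with 80% power under ANCOVA would keep between 80% and about 73% with all four visits in the model. All of this rests on assumed correlations, equal SDs over visits and complete-data algebra.

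It would be wrong to read this as bias or a threat to type I error: simulation showed neither to any material degree. The co-primary analyses and the sample size of 72 evaluable (80 enrolled) patients are unaffected. The redundancy of the random subject effect holds whatever the correlations are.

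**What to change.** In SAP 10.2.2.4, 10.2.2.5 and 10.2.2.6:

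1. Add a baseline-value-by-visit interaction.
2. State which visits enter each model, in particular whether week 2 does.
3. Delete the wording that makes subject a random effect, and keep subject as the block for the unstructured repeated-measures covariance.

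In SAP 7.9, describe the switch as a change of model and say that site is dropped and whether that is intended. Do this before unblinding.

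The interaction costs 3 degrees of freedom with weeks 2, 4, 8 and 12, or 2 with weeks 4, 8 and 12, and about 0-1% of variance if the slopes are in fact constant. Exact equality with a visit-specific ANCOVA on the same covariates would also need gender by visit and age class by visit. An alternative is to run the protocol's ANCOVA at each named week on every imputed data set. Either way the cost is SAP wording and a small programming change.
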